6 LIST OF ABBREVIATIONS AND DEFINITONS OF TERMS

AE	adverse event
AESI	adverse event of special interest
ALT	alanine aminotransferase
AST	aspartate aminotransferase
BFI	Brief Fatigue Inventory
BMI	body mass index
CI	confidence interval
CTx1	C-terminal telopeptide
CYP	Cytochrome
CYP19	aromatase
D	Day
DBP	diastolic blood pressure
DEXA	dual energy X-ray absorptiometry
DMC	Data monitoring committee
ECG	electrocardiogram
eCRF	electronic case report form
EDC	electronic data capture
eGFR	estimated glomerular filtration rate
EOT	End of Treatment
EUDRACT	European Union Drug Regulatory Agency Clinical Trial
FDA	Food and Drug Administration
FSH	follicle stimulating hormone
FU	Follow-Up
GCP	Good Clinical Practice
h	hour
HbA1c	glycosylated haemoglobin
HDL	high density lipoprotein
HH	hypogonadotropic hypogonadism
HOMA-IR	homeostatic assessment of insulin resistance
hs-CRP	high sensitivity C-reactive protein
IB	Investigator's Brochure
ICF	informed consent form
ICH	International Conference on Harmonisation
IEC	Independent Ethics Committee
IIEF	International Index of Erectile Function
INR	International Normalised Ratio
IRB	Institutional Review Board

IRT	interactive response technology
ITT	intention to treat
LDL	low density lipoprotein
LH	luteinising hormone
MedDRA	Medical Dictionary for Regulatory Activities
P1NP	procollagen type 1 N-propeptide
PGI-S	Patient Global Impression of Status
PK	pharmacokinetics
PRO	patient reported outcome
PROMIS	Patient-Reported Outcomes Measurement Information System
PSA	prostate-specific antigen
QoL	quality of life
QT _C	corrected QT interval
QT _C F	QT _C by Fridericia's correction method
RBC	red blood cell
SAE	serious adverse event
SAP	statistical analysis plan
SexFS	Sexual Function and Satisfaction
SF-36	36-item Short Form Health Survey
SHBG	sex hormone binding globulin
SBP	systolic blood pressure
SD	standard deviation
T _{1/2}	half-life
TEAE	treatment emergent adverse event
T _{max}	time at which maximum serum concentration is reached
ULN	upper limit of normal
W	week
WBC	white blood cell

7 INTRODUCTION

7.1 Background

Aromatase (CYP19) is highly expressed in adipose tissue, where it converts testosterone to oestradiol and androstenedione to oestrone. In human obesity, excess adipose tissue is associated with excess aromatase activity, resulting in higher levels of oestradiol in men and women. In obese men, the relative excess of oestradiol can feed back to the hypothalamic pituitary axis, suppressing gonadotropin secretion and thereby suppressing testicular testosterone production and spermatogenesis. Severe obesity is associated with relative androgen deficiency in men and epidemiologic data support the hypothesis that excess adipose tissue contributes to the pathogenesis of hypogonadotropic hypogonadism (HH) in obese men (Hofstra et al 2008).

There are many consequences of testosterone deficiency including decreased libido, erections and fertility, low bone mineral density, increased risk of fractures, decreased muscle mass and strength, fatigue, and impact on mood and cognition and loss of body hair (Bhasin et al 2006). Recent studies have also demonstrated that testosterone deficiency in older obese men is associated with metabolic abnormalities including insulin resistance, glucose intolerance, and lipid abnormalities, contributing to an increased incidence of metabolic syndrome and likely increased risk of cardiovascular disease (Kapoor et al 2006).

BGS649 is a potent aromatase inhibitor and a derivative of the marketed drug letrozole (Femara). It was conceived as a long half-life ($T_{1/2}$) aromatase inhibitor for the treatment of refractory endometriosis and is being evaluated in obese men with HH.

The safety and efficacy (in terms of normalisation of serum testosterone levels) of BGS649 in male obese subjects with HH is currently being evaluated in the ongoing Study MBGS205.

Use of aromatase inhibitors in women with breast cancer have been associated with reduction in bone mineral density and risk of fracture. This is attributed to the oestrogen lowering effects in post-menopausal women. The potential for BGS649 to affect bone in obese males with hypogonadism is expected to be less as oestrogen levels are similar to those in pre-menopausal women and only 25% oestradiol reduction was observed after 12 weeks of BGS649 0.3 mg loading dose and 0.1 mg weekly. There may be other factors that reduce sensitivity to aromatase inhibition on bone in this population as bone mineral density increases with increasing BMI, and bone anabolic effects are expected with the normalisation of testosterone.

Understanding any potential effect is a critical element to the risk/benefit profile of BGS649. Bone turnover biomarkers and bone mineral density are being assessed in MBGS205, however 6 months is too short duration to assess bone mineral density. Study MBGS206 will be a 6 month extension of Study MBGS205 to measure the effects of 12 months treatment with BGS649 on bone mineral density.

7.1.1 Aromatase Inhibitors and Bone

In the adult skeleton, bone remodelling is controlled by regulating the balance between the resorptive activity of osteoclasts and the bone-forming action of osteoblasts (Perez and Weilbaecher 2006). Normal bone turnover is maintained by a complex regulatory system involving both systemic and local factors. Oestrogen has suppressive, antiresorptive effects on osteoclasts during the process of bone remodelling; these effects are pleiotropic and largely indirect. Aromatase inhibitors block the peripheral conversion (aromatisation) of oestrogen from androgen precursors, thereby lowering tissue and circulating oestrogen levels. Treatment with aromatase inhibitors can decrease oestrogen levels and lead to excessive bone resorption. It has been associated with bone loss, decreased bone mineral density, and an increase in osteoporotic fractures. However, these effects have generally been observed in woman treated for breast cancer with high relative doses and long duration of treatment of the aromatase inhibitor and in post-menopausal women with low oestrogen levels (Mincey et al 2006).

Testosterone and oestradiol are critical for normal bone development and maintenance in men (Sinnesael et al 2011). However, there are limited data on aromatase inhibition in this population and none in the obesity-related HH population which is the target for BGS649 or with the lower levels of aromatase inhibition that is being developed within this dose-ranging study.

Bone mineral density was investigated in two studies in older men with low testosterone levels (Dias et al 2015, Burnett-Bowie et al 2009). The effects of a transdermal testosterone gel, anastrozole (an aromatase inhibitor) 1 mg daily, or placebo on body composition, bone mass, muscle strength, and gait speed were evaluated for 12 months in 43 older men with low testosterone levels (Dias et al 2015). Both transdermal testosterone and anastrozole increased serum testosterone levels (>500 ng/dL, $p < 0.05$) compared with baseline, and testosterone levels remained stable throughout the study. At 12 months, the primary outcome of lumbar spine bone mineral density increased compared with baseline in the transdermal testosterone and placebo groups ($p < 0.01$), and remained stable in the anastrozole group. The reason for the increase in bone mineral density in the placebo group was unclear and expected to have driven the statistical significance of the change in bone mineral density of anastrozole which was assessed relative to placebo. The effects of anastrozole 1 mg daily or placebo on bone mineral density and bone turnover were evaluated in a 1-year study in 69 older men with borderline or low testosterone levels and hypogonadal symptoms (Burnett-Bowie et al 2009). The aromatase inhibitor increased testosterone levels and moderately decreased oestradiol levels. Posterior-anterior spine bone mineral density decreased in the anastrozole group compared with the placebo group ($p = 0.0014$); there were no significant effects on bone mineral density at other anatomical sites. Bone turnover markers were not affected by anastrozole therapy. Therefore, aromatisation of testosterone may play a role in bone mineral density in older men with low testosterone levels.

Further understanding on the gonadal steroid-dependent effects on bone turnover and bone mineral density has come through investigation in healthy adult men aged 20-50 years (Finkelstein et al 2016). All volunteers were given goserelin acetate to suppress endogenous

gonadal steroid production. One cohort (198 men) were randomised to treatment with increasing concentrations of testosterone gel daily for 16 weeks. A second cohort (202 men) were randomised to receive these treatments together with anastrozole. A control group (37 men) were given placebo. The study supports other studies that a balance between oestrogen and testosterone is important. Although oestrogen may primarily regulate bone metabolism in adult men, in order to affect bone development, testosterone and oestradiol levels must decline substantially. Oestradiol levels above 10 pg/mL and testosterone levels above 200 ng/dL were generally sufficient to prevent increases in bone resorption and decreases in bone mineral density in men in this study, suggesting that in hypogonadism the elevation of testosterone in association with oestradiol above a threshold may enable maintenance or improvement of bone density.

7.1.2 Clinical Experience with BGS649

To date, 54 post-menopausal and 52 pre-menopausal women of non-childbearing potential have been exposed to single doses of BGS649 up to 20 mg. BGS649 showed a dose-dependent suppression of oestrone, which was maximal at 0.1 mg, and oestrone inhibition was sustained for more than 3 weeks after a single dose. There was no effect of BGS649 on cortisol metabolism, aldosterone synthesis, progesterone levels, androgen levels, urinary 17-keto, or 17-hydroxysteroids. However, BGS649 at the highest single doses of 10 and 20mg showed small but clinically significant decrease in bone density limited to the lumbar spine at 6 months.

To date, BGS649 has also been administered to 21 obese men with HH (8 subjects were assigned to placebo) (Study CBGS649A2204). This first-in-man study was a 2-part study over 12 weeks (11 treatments); Part 1 was an open-label dose-finding study (weekly, individually titrated doses) and Part 2 used a fixed dose regimen [REDACTED]. Overall, BGS649 treatment (n=21) resulted in normalisation and maintenance of serum total testosterone, with no evidence of total testosterone peaks above the upper limit of normal (ULN). Oestradiol levels were reduced by approximately 25-50%. There was no change in femoral neck bone mineral density and bone turnover markers after first or second part of the study. However, the second part of the study was underpowered and result not interpretable.

Study MBGS205 is an ongoing Phase IIb multicentre, double-blind, dose-ranging, randomised, placebo-controlled study evaluating the safety and efficacy of BGS649 in male obese subjects with HH. The primary objective of the study is to demonstrate the efficacy of BGS649 to normalise testosterone (to within normal lab-specific reference range i.e., total testosterone levels 300-1000 ng/dL [10.4-35 nmol/L]) in $\geq 75\%$ of a population of obese male subjects with HH after 24 weeks of double-blind treatment compared to placebo. As a part of safety objectives, study will evaluate effect of BGS649 on bone mineral density and bone turnover markers.

A complete review of data obtained to date on BGS649 is presented in the most recent Investigator's Brochure (IB) and Food and Drug Administration (FDA) guidelines have been

published on the use of testosterone replacement therapy (Testosterone Replacement Therapy, 2014).

7.2 Rationale/Discussion

7.2.1 Rationale for bone density safety study.

Bone density decrease is a class effect of aromatase inhibitors via a mechanism of decreased oestrogenic production. BGS649 has been shown to decrease oestrogen by 25-50%, potentially affecting the bone formation process and leading to osteoporosis (Study CBGS649A2204). In a single dose study in post-menopausal women, BGS649 at the highest doses of 10 and 20 mg showed a small but clinically significant decrease in bone density limited to the lumbar spine at 6 months. In clinical studies to date there has been no consistent effect of BGS649 on bone resorption biomarkers and no effects of BGS649 on bone density were demonstrated at 12 weeks in the previous study in males with HH. However, the effects of long-term treatment with BGS649 in male obese subjects with HH have not been investigated.

Men with hypogonadism have low testosterone that is associated with a decrease in bone mineral density. However, men with obesity related HH may have oestrogen levels similar to the levels in pre-menopausal women. In addition, obesity has protective effect on the bone mineral density so the risk associated with aromatase inhibitor treatment may be attenuated (Zhao et al 2007).

Study MBGS206 will investigate the effect of BGS649 on bone mineral density after a 12 month period of treatment with active study drug (6 months treatment during Study MBGS205). The overall 12 months exposure with BGS649 in the obese male HH patient should be an adequate duration of the aromatase inhibitor therapy to detect a change in bone mineral density to better define the risk/benefit of BGS649 in the obese male HH patient (Dias et al 2015; Burnett-Bowie et al 2009). The study is powered to detect a 3% decrease from Baseline in lumbar bone mineral density measured in g/cm² by dual energy X-ray absorptiometry (DEXA) at 48 weeks (Kacker et al 2014).

Rational for other study considerations:

The doses of BGS649 [REDACTED] and dosing schedule [REDACTED] selected for use in Study MBGS205 were chosen based on results obtained in a previous study in obese male subjects with HH, which suggested that these doses were well tolerated and may normalise testosterone levels (Study CBGS649A2204). To assure 12 months each dose arm study drug exposure, subjects will continue with the same active study drug assignment from Study MBGS205 to the Study MBGS206. To keep the study blinded and offer subjects receiving placebo the benefit of active arm treatment, the placebo subjects in Study MBGS205 will be randomised to one of the active treatment arms. If one or more dosing arms are dropped during the conduct of Study MBGS205, these will not be progressed in Study MBGS206.

Aromatase inhibitors decrease oestrogen synthesis and increase pituitary luteinising hormone (LH) and follicle stimulating hormone (FSH) with a consequent stimulation of testosterone

production (de Boer et al 2005; Loves et al 2008). This increase in testosterone has multiple clinical effects, including: effect on insulin resistance, on body composition, strength and sexual and overall well-being. Therefore, additional safety, efficacy, and pharmacokinetic (PK) will be collected in subjects who completed the full 24 week treatment period in Study MBGS205. It is conceivable that up to 12 month exposure may be needed to demonstrate full treatment benefit in regards to positive effect on cardiometabolic parameters (Haider et al 2010). In addition, the improvement in body composition may be also shown consistently only after 12 months treatment (Emmelot-Vonk et al 2008).

Testosterone increase may lead to worsening certain parameters e.g. prostate-specific antigen (PSA), haematocrit. To ensure adequate safety monitoring, these parameters together with testosterone level will be monitored in the same way as in MBGS205 study (see Section 9.1.1 for a detailed description)

BGS649 has been shown to be present in semen. PK assessment of seminal fluid and plasma will be performed to determine the plasma/semen relationship to enable modelling of BGS649 semen concentration by dose in order to determine the potential transference of BGS649 to sexual partners.

This study will be conducted in compliance with the protocol and with the International Conference on Harmonisation (ICH) guidelines on Good Clinical Practice (GCP).

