
Name of Sponsor/Company: Mereo BioPharma 2 Ltd	Individual Study Table Referring to Part of the Dossier:	(For National Authority Use Only)
Name of Product: BGS649		
Name of Active Ingredient: 4,4'-[fluoro-(1-H-1,2,4-triazol-1-yl)methylene]bisbenzotrile	Volume: Page:	
Treatment allocation Subjects receiving active doses of BGS649 in Study MBGS205 will continue with the same dose in Study MBGS206. Subjects receiving placebo in Study MBGS205 will be randomised, using interactive response technology (IRT), on a 1:1:1 basis to each of the following active treatment arms: 
 • BGS649 [REDACTED] • BGS649 [REDACTED] • BGS649 [REDACTED] If one or more dosing arms are dropped during the conduct of Study MBGS205 these will not be progressed in Study MBGS206 and subjects switching from placebo will be randomly allocated to available dose arms.		
Number of Subjects: Enrolment will continue until 30 subjects from each of the previous active treatment arms in Study MBGS205 have entered this study aiming for approximately 25 subjects completing each dose level with 48 weeks total exposure. Assuming about 17% dropout rate in the extension study. Subjects previously treated with placebo will be enrolled until target subject population is met in all active arms.		

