
Statistical Methods:
 
Populations to be analysed:
 
The intention to treat (ITT) population includes all subjects who:
 
 1. Are randomised, and 2. Receive at least 1 dose of study medication, and 3. Provide a Baseline efficacy value and at least 1 available evaluation of efficacy post-Baseline. 
The safety population includes all subjects who received at least 1 administration of the study medication.
 
For the summary of semen concentration of BGS649, all subjects who received at least 1 administration of the study medication and have at least 1 quantifiable concentration will be included in the PK population.
 
All safety endpoints will be analysed using the safety population. All efficacy endpoints will be analysed using the ITT population.
 
Further safety and tolerability will be analysed using the safety population.
 
Primary Statistical Hypothesis: The percentage decrease from Baseline in lumbar bone mineral density measured in g/cm² by DEXA [REDACTED]
 
H0: ≤ 3%
 
H1: > 3%
 
The null hypothesis will be rejected for a dose group and the endpoint considered met if the lower bound of the 2-sided 95% confidence interval for the percentage decrease from Baseline in lumber spine is greater than 3%.
 
Assuming a 2-sided test at [REDACTED] significant level and a standard deviation of [REDACTED] to achieve 90% power N=25 subjects in each dose group would be needed to detect a [REDACTED] decrease from Baseline in bone mineral density at 48 weeks.
		
Date of the Protocol: Amended Version 2.0, 28 Mar 2017		

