13 STATISTICAL EVALUATION

13.1 Sample Size and Power

Primary Statistical Hypothesis: The percentage decrease from Baseline in lumbar bone mineral density measured in g/cm² by DEXA within a dose group is greater than [REDACTED]

H0: ≤ 3%

H1: > 3%

The null hypothesis will be rejected for a dose group and the endpoint considered met if the lower bound of the 2-sided 95% confidence interval (CI) for the percentage decrease from Baseline in lumbar spine is greater than [REDACTED].

Assuming a 2-sided test at 5% significant level and a standard deviation (SD) of 0.0439 g/cm², to achieve 90% power N=25 subjects in each dose group would be needed to detect a [REDACTED] decrease from Baseline in bone mineral density at 48 weeks.

Enrolment will continue until 30 subjects from each of the previous active treatment arms in Study MBGS205 have entered this study. Subjects previously treated with placebo will be enrolled until target subject population is met in all active arms.

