13.5.2 Analysis of Primary Endpoint

The percentage change from Baseline in lumbar bone mineral density measured in g/cm² by DEXA will be summarised by dose group and visit. A single sample 1-sided t-test conducted at the 2.5% significance level will be used to analyse percentage change from Baseline (MBGS205) at Week 48 (MBGS206) in each treatment arm to test the null hypothesis that the percentage decrease from Baseline is $\leq 3\%$. Only subjects that have a post-Baseline DEXA assessment in MBGS206 will be included in this analysis.

The primary analysis will be performed using the safety population.

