13.5.3 Analysis of Secondary Endpoints

13.5.3.1 Safety

The analysis of secondary safety endpoints will be performed using the safety population.

The percentage change from Baseline in hip bone mineral density measured in g/cm² by DEXA will be summarised by treatment arm and visit. A single sample 1-sided t-test conducted at the 2.5% significance level will be used to analysis percentage change from Baseline (MBGS205) at Week 48 (MBGS206) in each treatment arm to test the null hypothesis that the percentage decrease from Baseline is $\leq 3\%$. Only subjects that have a post-Baseline DEXA assessment in MBGS206 will be included in this analysis.

The percentage change from Baseline in bone turnover markers, bone density, bone biomarkers and oestradiol (absolute and percentage) will be summarised by treatment arm and visit. A 95% CI will be presented for the mean change at each visit.

The proportion of subject with a T-score ≤ -2.5 at Week 48 will be summarised by treatment arm and visit. A 95% CI will be presented for the proportion of subjects with a T-score ≤ -2.5 .

The proportion of subjects with testosterone ≤ 1000 ng/dl (35 nmol/L) and > 1000 ng/dl (35 nmol/L) will be summarised by treatment arm and visit.

TEAEs will be summarised per [Section 13.5.5](#). For subjects randomised to active treatment in Study MBGS205 first dose is considered as the first dose in Study MBGS205. For subjects randomised to placebo in Study MBGS205 first dose is considered as the first dose in Study MBGS206.

A more detailed description will be presented in the SAP.

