#### 8.6.2 Analysis of primary endpoint

The Primary Endpoint is defined as the change in lumbar bone density measured by DEXA from baseline in Study MBGS205 to Week 48 in Study MBGS206 by dose group in subjects randomised to active treatment in Study MBGS205.

DXA Scan assessments will only be performed at the EOT visit (for subjects that reached at least Week 36) and will be over-read by IMI. The DEXA over-read data will be used for the primary endpoint statistical analysis.

Descriptive statistics (observed values, changes from baseline and percentage change from baseline) in lumbar bone mineral density will be presented for each treatment regimen and time-point. A single sample 1-sided t-test conducted at the 2.5% significance level will be used to analyse percentage change from Baseline (MBGS205) to Week 48 (MBGS206) LOCF in each treatment arm to test the null hypothesis that the percentage decrease from Baseline is  $\leq 3\%$ . P-values and associated CI will be presented.

Only subjects included in the safety population that have a post-Baseline DEXA assessment in MBGS206 and were randomised to active treatment in Study MBGS205 will be included in this analysis. The analysis will be repeated for subjects included in the completer population.

Observed and percentage change from baseline values at each visit will be presented in a line graph by treatment group.

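### Protocol 7.2.1 says the study is powered for a 3% lumbar bone loss, but 3% is the null boundary of the primary test, so power there is 2.5%; and no stated rule can show a loss below 3%

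*Protocol*

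**What the plan says.** The rationale in Protocol 7.2.1 states that "The study is powered to detect a 3% decrease from Baseline in lumbar bone mineral density" at 48 weeks. It is the only readable statement of the effect the study is powered for.

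The hypotheses in the synopsis and Protocol 13.1 are H0: decrease ≤ 3% and H1: decrease > 3%. The null is rejected for a dose group, and the endpoint counted as met, if "the lower bound of the 2-sided 95% confidence interval for the percentage decrease from Baseline in lumber spine is greater than 3" per cent. Protocol 13.5.2 specifies a single-sample, 1-sided 2.5% t-test "to test the null hypothesis that the percentage decrease from Baseline is" at most 3%. SAP 8.6.2 keeps it: "A single sample 1-sided t-test conducted at the 2.5% significance level will be used to analyse percentage change from Baseline", and adds "P-values and associated CI will be presented". Protocol 13.5.3.1 applies the same null to the hip, "in each treatment arm to test the null hypothesis that the percentage decrease from Baseline is" at most 3%.

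The sample size text in Protocol 13.1 assumes a "standard deviation (SD) of 0.0439 g/cm², to achieve 90% power N=25 subjects in each dose group would be needed". The decrease to be detected is blacked out in that sentence. The synopsis has 30 men per previous active arm entering, "aiming for approximately 25 subjects completing each dose level with 48 weeks total exposure", with about 17% dropout.

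**The concern.** A test has power to detect an effect only if that effect lies inside its alternative hypothesis. Here 3% is the edge of the null, so a study powered for a 3% loss and a test whose null is a loss of at most 3% do not fit together. A reader of 7.2.1 would think that a 3% loss is very likely to be flagged, when the written test would almost never flag it.

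The second issue is what a negative result means. The study exists to define the bone risk of a drug whose class is known to reduce bone density. The only formal rule has two outcomes: a loss above 3% is shown, or it is not. The second covers both a loss convincingly below 3% and an estimate too imprecise to tell. Without a stated reading, non-rejection can be taken as reassurance that the data do not give.

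**Working it through.** **Inputs from the documents.** Null boundary 3%; one-sample t-test, 1-sided 2.5% (the same upper cut-off as the 2-sided 5% in 13.1); SD 0.0439 g/cm²; N = 25 for 90% power; 30 entering per arm. The dropout figures agree: 30 × 0.83 = 24.9, about 25. Men who stop early after Week 36 are still scanned (Protocol 12.4), so between 25 and 30 may be analysed.

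**Inputs the documents do not give.** Whether 0.0439 g/cm² is the SD of within-man change or of the density level, and the mean baseline density needed to convert it to the percentage scale of the endpoint. Where needed, I assume it is the SD of change and that mean baseline b is 0.9 to 1.3 g/cm². Then SD(%) = 4.39 / b, which is 4.88% at 0.9, 4.39% at 1.0 and 3.38% at 1.3.

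**Step 1: where N = 25 could come from.** Power is P(T > t₀.₉₇₅,ₙ₋₁), with T noncentral t and noncentrality √n × (true loss − null value) / SD.
- 3% against a null of zero at b = 1.0: noncentrality √25 × 3 / 4.39 = 3.42 and power 90.6%. N = 25 is the smallest n that reaches 90%. At b = 0.9, 1.0, 1.1, 1.2 and 1.3 the smallest n is 30, 25, 21, 18 and 16.
- The written null of 3% at b = 1.0: N = 25 gives 90.6% power at a true loss of 6%.

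Both cases give the same N because both are a 3-point distance. The documents do not say which was used.

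**Step 2: power of the written test at a true 3% loss.** The noncentrality is √n × (3 − 3) / SD = 0, so T follows the ordinary t distribution and the rejection probability is 2.5%. It does not depend on n, SD or b. Simulation with normal data, n from 10 to 1,000 and SD of 2, 4.39 and 8%, gave 2.2 to 2.7%.

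**Step 3: true loss needed for 90% power.** Solving for the standardised distance gives 0.676 SD with 25 analysed and 0.612 SD with 30. At b = 1.0 and n = 25 this is 3 + 0.676 × 4.39 = 5.97%.

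| Analysed | b (g/cm²) | Power, true 4% | Power, true 5% | True loss for 90% power | Observed mean loss needed to reject |
|---|---|---|---|---|---|
| 25 | 0.9 | 16.5% | 50.3% | 6.30% | 5.01% |
| 25 | 1.0 | 19.3% | 58.9% | 5.97% | 4.81% |
| 25 | 1.3 | 29.5% | 81.1% | 5.28% | 4.39% |
| 30 | 0.9 | 19.1% | 58.4% | 5.99% | 4.82% |
| 30 | 1.0 | 22.6% | 67.4% | 5.69% | 4.64% |
| 30 | 1.3 | 34.8% | 88.0% | 5.07% | 4.26% |

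The last column is 3 + t₀.₉₇₅,ₙ₋₁ × SD / √n, with SD at its assumed value; for n = 25 and b = 1.0, 3 + 2.064 × 4.39 / 5 = 4.81.

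**Step 4: what non-rejection can mean.** At b = 1.0 with 25 analysed, the test fails to reject with probability 81% at a true 4% loss and 41% at a true 5% loss. At a true loss of 2% or 4% the 2-sided 95% interval still contains 3% with probability 70 to 83% (25 analysed) or 65 to 81% (30 analysed). The upper bound can still be informative: with 25 analysed it falls below 3% with probability 84 to 99% if the true loss is zero and 50 to 81% if it is 1%.

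**The case against.** The sentence in 7.2.1 is background prose with no alpha, N or SD, and may be loose shorthand for the 3% threshold in the hypotheses. The 90% figure stands in 13.1, where the effect is redacted, so 13.1 may be right. Every test rejects at its boundary with probability alpha, so the 2.5% is no defect of this design. It also assumes normality: a simulation with strongly skewed data at n = 25 gave about 0.6% or 7%, depending on the direction of skew. The other power figures rest on an SD meaning and a baseline that the documents do not state.

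On the second part, the rule is built to flag harm, and nowhere do the documents claim that non-rejection shows a loss of 3% or less. All analyses are labelled exploratory (Protocol 13.5.1). A confidence interval is planned for the primary test, and Protocol 13.5.3.1 plans one for the mean change in bone density at each visit. A reader can compare the upper bound with 3% unaided.

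Much of this stands as a limit on severity. The test itself is coherent, 13.1 cannot be called wrong, and the figures in the table are illustrations. But even as shorthand the sentence names an effect for which the written test has no useful power, and no value of the redacted effect makes it true of this test. The interval is planned without any statement of how to read it. The other bone readouts (the proportion with T-score ≤ −2.5, the severity shift table, the MMRM) carry no criterion for a loss below 3% either.

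**Conclusion.** The concern holds. For the written test, power at a true 3% loss is 2.5% per dose group. This needs no figure beyond the stated null and alpha, and is exact for the t-test under normality. Protocol 7.2.1 is therefore wrong as written; whether 13.1 is also wrong depends on the redacted effect.

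How far above 3% the loss must be is 0.68 SD with 25 analysed or 0.61 SD with 30. Only under the assumed SD meaning and baseline range does this become a true loss of about 5.3 to 6.3% or 5.1 to 6.0%.

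The decision rule can show a loss above 3%, and no stated criterion can show one below it, for spine or hip. This should be fixed. It is a correction of wording and interpretation, not a failed design.

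**What to change.** 1. Correct Protocol 7.2.1 to agree with 13.1. State the true loss at which power is 90% against the 3% null, what the SD of 0.0439 g/cm² describes, and its value on the percentage-change scale. If N = 25 was derived for 3% against zero, restate the power of the written test.
2. State in Protocol 13.5.2 and SAP 8.6.2, and for the hip in Protocol 13.5.3.1, that failure to reject is not evidence that the loss is 3% or less.
3. Fix the reading of the 2-sided 95% interval for the percentage decrease in each dose group: lower bound above 3%, a loss above 3% is shown; upper bound below 3%, a 3% loss is excluded; otherwise inconclusive.

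Sample size, data, test and primary hypothesis do not change. The cost is a less favourable power statement. Timing matters for item 3: SAP 3.2.3 breaks the MBGS206 blind for sponsor and CRO when MBGS205 is unblinded, and the documents do not give that date. A reading rule added after it must be reported as post hoc.
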